4.2 JOINT INCLUSION CRITERIA FOR ALL EPOS TRIALS AT BASELINE COLONOSCOPY

[figure not shown]
- * Men and women age 40-74 years
- * Cecal intubation (preferably documented by images/video of the appendiceal orifice and the ileocecal valve; but not required).
- * Adequate colonic cleansing, with Boston Bowel Cleansing Score equal or higher than 2 points in all colonic segments.
- * Complete excision of all polyps at baseline colonoscopy findings (as judged by the trial endoscopists)
- * Randomisation must be performed no longer than 26 weeks (182 days) from completion date of baseline colonoscopy

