4.3 SPECIFIC DESIGNS AND SETTINGS

4.3.1. EPoS I

Eligible individuals are persons with low-risk adenomas removed at baseline colonoscopy (1-2 tubular adenomas size <10mm with low-grade dysplasia) and no serrated polyps with dysplasia, with diameter 10 mm or larger at any location or with diameter 5 mm or larger proximal to the splenic flexure.

Individuals will be **randomized** into one of two intervention groups:

Group 1: Surveillance colonoscopy at 5 and 10 years after baseline colonoscopy.

Group 2: Surveillance colonoscopy at 10 years after baseline colonoscopy.

The primary and secondary endpoints will be analyzed directly after the 10 year surveillance colonoscopy, (figure 1).

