11. STATISTICAL ANALYSIS PLAN

Participants are followed for the primary endpoint (incidence of CRC), until death/incidence of CRC or end of follow-up, whichever happens first. All randomised participants are followed up through national or regional registries, regardless of whether they continue in the study or not. The primary analytic approach of the trial will follow the intention-to-treat (ITT) principle. We will compare the ~~average rate~~

~~of differences for~~ each endpoint between the intervention groups by calculating risk differences and log-rank test ~~fitting a Cox proportional hazards model~~. The limit for the statistical significance will be established in 0.05 and 95% confidence intervals will be calculated. If the distribution of any baseline characteristics is found to be imbalanced between the arms, we will conduct a sensitivity analysis in which those characteristics will be included as covariates in the model.

We will also do analyses to estimate the causal effect that would have been observed if all individuals in the intervention arms had been compliant. We will refer to these analyses as “adherence-adjusted” analyses. We will use two different analytic approaches to obtain “adherence-adjusted” estimates: instrumental variables methods and inverse probability weighting. For comparability, we will translate the estimates from both approaches into a common metric: adjusted (CRC-free) survival curves. To implement instrumental variables methods (with the indicator for treatment arm as the instrument), we will use g-estimation of nested structural models. To implement inverse probability weighted estimation, we will estimate the weights and the parameters of a marginal structural Cox model. The estimation of inverse probability weights in one intervention arm requires the measurement of variables that jointly predict compliance with the baseline intervention and the endpoint. These variables include age, sex, baseline findings, physical activity, family history of colorectal cancer, smoking status, use of aspirin, NSAIDs, and hormone replacement therapy (9).

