11. SAMPLE SIZE CALCULATION

Assuming a risk of CRC of 1% at 10 years for patients with low risk adenoma and of 2% for patients with high-risk adenomas at baseline and using a non-inferiority hypothesis with an equivalence interval of 0.5% for patients with low risk adenomas and 0.7% for patients with high risk adenomas, we need to include 6,783 individuals in each arm of the EPoS I trial, and 6,852 in each arm of the EPoS II trial. That supposes a total of 13,566 individuals randomized in the EPoS I and 13,704 in the EPoS II trial (with a power of 90% and a one-sided alpha of 0.05, see table).

The table shows power scenarios for 80% and 90% power for EPoS I and II, respectively.

Table 2: Power Analysis for EPoS I and EPoS II, based on non-inferiority tests of two independent proportions.

	Power	10 year CRC incidence (proportion)		Group size	Total sample size
		P1 proportion	P2 proportion		
EPoS I	80%	0.01	0.015	4897	9794
EPoS I	90%	0.01	0.015	6783	13566
EPoS II	80%	0.02	0.027	4947	9894
EPoS II	90%	0.02	0.027	6852	13704

P1 is the control group (shorter surveillance intervals), P2 is the intervention group (longer surveillance intervals).

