- Thirdly, colonoscopy is costly and resource demanding. As a corollary, resources saved by less frequent surveillance of adenoma patients might convey greater public health benefit if used for other purposes in the health care system.
- Fourthly, the level of inferiority considered acceptable need and should not be the same in EPoS I as in EPoS II. Instead, we argue that a slightly higher absolute difference (inferiority) in cumulative incidence of colorectal cancer would be justifiable in EPoS II. This argument is based on the fact that in EPoS II, subjects randomized to less intense surveillance are spared one or probably two colonoscopies during a 5-year period compared with currently applied guidelines. In contrast, subjects enrolled in the EPoS I trial would be spared only one colonoscopy over a 10-year period.

In conclusion, based on the arguments outlined above, and acknowledging that any defined level of inferiority can be considered arbitrary, we have accepted an equivalence level of 0.5% in absolute colorectal cancer incidence in EPoS I, and of 0.7% in EPoS II. This implies that the null hypothesis of non-inferiority would be

rejected only if the upper limit of the 95% confidence interval for the absolute difference in cumulative incidence of colorectal cancer after ten years of follow-up exceeds 0.5% in EPoS I and 0.7% in EPoS II.

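### EPoS I reads its primary endpoint right after the year-10 exam, so undiagnosed cancers in people who skip it count as CRC-free, probably more often in the longer-interval arm; the bias is toward non-inferiority and of unknown size

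*Protocol*

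**What the plan says.** Section 4.3.1 of the Protocol sets out the two EPoS I arms: "Group 1: Surveillance colonoscopy at 5 and 10 years after baseline colonoscopy" and "Group 2: Surveillance colonoscopy at 10 years after baseline colonoscopy". The same section fixes when the endpoint is read: "The primary and secondary endpoints will be analyzed directly after the 10 year surveillance colonoscopy".

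Section 11 (statistical analysis plan) makes the primary analysis intention-to-treat and says: "All randomised participants are followed up through national or regional registries, regardless of whether they continue in the study or not". It follows each person until CRC, death or the end of follow-up, and gives no date for that end. It also plans adherence-adjusted analyses by instrumental variables and inverse probability weighting.

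Section 11.1 rests the decision on the "absolute difference in cumulative incidence of colorectal cancer after ten years of follow-up", with these margins: "we have accepted an equivalence level of 0.5% in absolute colorectal cancer incidence in EPoS I, and of 0.7% in EPoS II". Section 11 (sample size calculation) starts from "Assuming a risk of CRC of 1% at 10 years for patients with low risk adenoma".

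Section 7 provides a second reminder for people who do not book their exam. No section states an expected attendance rate at year 10.

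**The concern.** In EPoS I the year-10 colonoscopy is part of the assigned schedule and also the main way in which cancers still silent at year 10 become diagnosed. A registry cannot record a cancer that nobody has found. With the reading taken straight after the exam, a non-attender with a silent cancer enters the analysis as CRC-free.

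Equal loss in both arms would do little harm to the difference. The losses are unlikely to be equal, because the year-5 exam clears silent cancers and precursors in Group 1 only, while Group 2 has had no protocol exam since baseline. The same share of missed exit exams would then remove more events from Group 2. The observed difference moves down, and a longer interval that is truly at the margin is declared non-inferior more often than the nominal rate.

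EPoS II (section 4.3.2) has the same timing, but both of its arms are examined at year 5, so the mechanism has little to act on there.

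**Working it through.** **The plan's own figure.** For 1% in both arms, a 0.5-point margin, one-sided alpha 0.05 and 90% power: n = (1.645 + 1.282)² × 2 × 0.01 × 0.99 / 0.005² = 6,782.6, so 6,783 per arm. This agrees with Table 2. The total of 13,566 is exactly 2 × 6,783, with no addition for missed exams.

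**Decision rule.** Non-inferiority is taken as declared when the upper 95% limit of the risk difference (RD) lies below 0.5 points: P(NI) = Φ((0.5 − RD)/SE − 1.96). With true risks of 1.0% v 1.5% and full ascertainment, SE = √[(0.01 × 0.99 + 0.015 × 0.985)/6,783] = 0.191 points and P(NI) = 2.5%. Section 11 (sample size calculation) uses one-sided 0.05; at that level 1.645 replaces 1.96 and the nominal rate is 5%.

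**Assumptions (none is in the documents).** Silent cancer starts at a constant 0.15% a year and stays silent for an exponential time with mean m. The exam is fully sensitive. After a year-5 exam, later onset falls by two thirds to 0.05% a year. The totals are then 5 × 0.15 + 5 × 0.05 = 1.0% in Group 1 and 10 × 0.15 = 1.5% in Group 2.

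**Silent cancer at year 10.**
- Group 2: s2 = 0.15% × m × (1 − exp(−10/m)) = 0.43% for m = 3, 0.65% for m = 5.
- Group 1, examined at year 5: s1 = 0.05% × m × (1 − exp(−5/m)) = 0.12% for m = 3, 0.16% for m = 5.

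**Observed difference.** Let q be the share missing the exit exam in each arm and a the share of Group 1 exit-skippers who did attend year 5. A Group 1 member who missed both exams carries the same burden as a Group 2 skipper. With the true difference held at 0.50 points:

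RD = 0.50 − q × s2 + q × [a × s1 + (1 − a) × s2]

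For q = 20%, a = 1, m = 3: 0.50 − 0.087 + 0.024 = 0.44 points; SE recomputed from the observed risks is 0.187; P(NI) = 5.2%.

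| Group 1 exit-skippers who attended year 5 (q = 20%) | RD, m = 3 | P(NI) | RD, m = 5 | P(NI) |
|---|---|---|---|---|
| all | 0.44 | 5.2% | 0.40 | 7.7% |
| half | 0.47 | 3.7% | 0.45 | 4.5% |
| one in five | 0.49 | 2.9% | 0.48 | 3.2% |
| none | 0.50 | 2.5% | 0.50 | 2.5% |

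At one-sided 0.05 the first row becomes 9.5% (m = 3) and 13.3% (m = 5), against 5%.

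**Varying the other inputs, results for m = 3 (m = 5).**
- All Group 1 skippers attended year 5, 10% missed: 3.6% (4.5%). With 30% missed: 7.3% (12.5%).
- Unequal attendance, same premise: 40% missed in Group 1 and 20% in Group 2 gives 4.0% (5.5%). The bias cancels only when Group 1 misses s2/s1 = 3.6 (4.1) times as often.
- Year-5 removal does not change later onset: s1 becomes 0.15% × m × (1 − exp(−5/m)) = 0.37% (0.47%). The gap between arms is then only 0.07 (0.17) points, and 20% non-attendance moves the difference by 0.014 (0.035) points.

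**The case against.** **The larger figures are an extreme.** They pair perfect year-5 attendance with 20% absence at year 10. People who skip the exit exam are likely to be, in part, those who skipped year 5, and for them the difference between arms disappears. This stands. A reader might infer from the first row of the table that the false-positive rate doubles or triples. The documents do not support that: it is the upper end for equal attendance and also needs the assumed two-thirds cut in onset. Even then the 3-year case moves the difference by 0.06 points, about a third of a standard error.

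**The adherence-adjusted analyses already cover it.** Partly. The planned weighting uses similar covariates, and compliance could be read to include the year-10 exam. But section 11 does not say that those analyses address exit-exam ascertainment or tie them to the margin. Using arm as an instrument does not restore an undiagnosed outcome.

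**An undiagnosed cancer is not an incident case.** On a strict registry definition this is fair, and section 11.1 itself raises overdiagnosis. Yet attenders' silent cancers are counted and non-attenders' are not, so the endpoint depends on attendance.

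**This is detail for the SAP.** The supportive analyses might be placed there. The timing rule is stated in the Protocol.

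**Non-attendance is assumed.** True. Entry is open to "Men and women age 40-74 years", so an exit exam can fall at age 84, and section 7 foresees people who do not book. A reader might infer that substantial non-attendance is built in; an age limit and a reminder rule do not establish a rate.

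**Conclusion.** The concern holds as a directional bias of unknown size, confined in practice to EPoS I. It follows from three things the Protocol fixes: the reading taken straight after the year-10 exam, registry counting of diagnosed cancer, and a year-5 exam in Group 1 only. That Group 2 holds more silent cancer is an inference. It fits section 11.1, which regards fewer cancers under less surveillance as implausible.

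At the margin, with 20% of exit exams missed, the model puts false non-inferiority between 2.5% and 5.2% for a 3-year mean silent phase and between 2.5% and 7.7% for a 5-year one. The position within each range depends on how far year-5 and year-10 absences fall on the same people. The direction needs broadly similar exit attendance in the two arms; much poorer attendance in Group 1 could cancel it. The Protocol does not show that the primary analysis is invalid or that a non-inferiority finding would be false. It does leave a favourable result open to a question that is cheap to answer if planned in advance.

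**What to change.** Keep the 10-year ITT analysis as primary. Add to section 11 (statistical analysis plan), before outcome data are seen, as supportive analyses for EPoS I:

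1. Exit-exam attendance by arm, and a 10-year risk difference in which non-attenders alive and CRC-free at year 10 are represented by weighted attenders of the same arm. The weights should include year-5 attendance and findings in Group 1. State that this targets outcome ascertainment and is separate from the adherence-adjusted analyses. Compare it with the 0.5-point ten-year margin.
2. The ITT risk difference repeated after a fixed further period of registry follow-up, for example 3 years, reported with its confidence interval. Use it to judge the direction and size of any change. Do not apply the 0.5-point margin as a pass/fail rule, because section 11.1 defines that margin at ten years.

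Report any material disagreement with the main result as a limit on the non-inferiority conclusion. A rule requiring all the analyses to agree is not advised, since its power has not been assessed.

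The cost is wording and one later registry linkage, with no extra procedure and no delay to the main result. The later reading arrives about 3 years after it and includes some new cancers. In the model it surfaces only 1 − exp(−3/m) of the missed ones: 63% for m = 3 and 45% for m = 5.

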4.3.2 EPoS II

Eligible individuals are persons with high-risk adenomas removed at baseline colonoscopy (three to ten adenomas; or one or more adenoma w/size \geq 10mm, or one or more adenoma with high-grade dysplasia or villous growth pattern).

Individuals will be **randomized** into one of two intervention groups:

Group 1: Surveillance colonoscopy 3 and 5 years after baseline colonoscopy

Group 2: Surveillance colonoscopy 5 years after baseline colonoscopy

Feb 11th 2017

Individuals in both group 1 and group 2 will be subjected to a final colonoscopy surveillance after 10 years (figure 1).

The primary and secondary endpoints will be analysed directly after the 10 year surveillance colonoscopy, (figure 1). A secondary analysis will be performed after the 5 year colonoscopy.

For centers with current guidelines for 1 year surveillance for multiple or large (>20mm) adenomas; they may exclude those patients.

In both EPoS I and EPoS II, surveillance intervals after the first surveillance colonoscopy take into account findings at the first surveillance colonoscopy. Surveillance intervals after first surveillance colonoscopy are shown in **Figure 2A (EPoS I) and-B (EPoS II)**.

Figure 2. Surveillance intervals after first follow-up colonoscopy in EPoS I and II

Figure 2A: EPoS I

[figure not shown]
[figure not shown]

Figure 2B; EPoS II

LRA: Low risk adenoma; HRA: High-risk adenoma

Figure 2C: Polyp characteristics and eligibility in EPoS. SP: Serrated polyp, TSA: Traditional Serrated Adenoma.

Serrated polyp	≥10mm SP and/or SSA with dysplasia and/or TSA	≥5mm SP in the proximal colon	<10mm SP with no dysplasia in the distal colon	<5mm SP with no dysplasia in the proximal colon	None
No adenoma	EPoS III	EPoS III	No inclusion	No inclusion	No inclusion
1-2 tubular adenoma <10mm with low-grade dysplasia	EPoS III	EPoS III	EPoS I	EPoS I	EPoS I
>2 adenoma	EPoS II	EPoS II	EPoS II	EPoS II	EPoS II
Villous histology	EPoS II	EPoS II	EPoS II	EPoS II	EPoS II
High grade dysplasia	EPoS II	EPoS II	EPoS II	EPoS II	EPoS II
Adenoma ≥10mm	EPoS II	EPoS II	EPoS II	EPoS II	EPoS II

4.3.3. EPoS III;

Individuals are eligible if they have one or more serrated polyps (defined as polyps which are non-adenomatous; including hyperplastic polyp, sessile serrated adenomas/polyps (without and with dysplasia), and traditional serrated adenomas) ≥ 10 mm in diameter at any colorectal location, or one or more serrated polyps ≥ 5 mm if located proximal to the splenic flexure removed at baseline colonoscopy. Individuals are also eligible for EPoS III if they have at least one serrated polyp with dysplasia, irrespective of size.

Patients with adenomas eligible for EPoS and

- 1) serrated polyps with dysplasia or
- 2) serrated polyps 10 mm or larger in any location
- 3) serrated polyps 5 mm or larger proximal to the splenic flexure will be included in EPoS III. ~~I and at Patients with serrated polyps AND adenomatous polyps are NOT eligible for EPoS III but they can be randomized for EPoS I or II according to the characteristics of their adenomatous polyps.~~ Patients with adenomas eligible for EPoS II and serrated polyps will be eligible for EPoS II. The data of these patients will

also be used for the EPoS III endpoint “yield of advanced neoplasia during surveillance colonoscopy after serrated polyp excision”.

Colonoscopy will be repeated at 5 and 10 years in all individuals in order to quantify CRC incidence and the yield of surveillance colonoscopy in detecting advanced neoplasia. Findings in surveillance colonoscopies will be compared with those obtained in the EPoS I and II trials.

5. VARIABLES OF INTEREST

For the detailed list of variables gathered in the trials, see the “List of variables” document attached

6. RANDOMIZATION

Randomization and data management will be done centrally for this trial. Eligible individuals will be invited to participate in the study and provide written informed consent prior to randomisation. Randomisation must be performed within 26 weeks (182 days) from baseline colonoscopy. Central randomization into the relevant trial (EPoS I, II or III) will be done using the Frontier Science randomisation system for all subjects, depending on their polyp characteristics. Subjects in EPoS I and II will be assigned to a corresponding treatment arm in a 1:1 ratio, depending on the additional stratification factors of site, age and sex.

7. FOLLOW-UP APPOINTMENTS

Local centres will send out follow-up invitations before the scheduled surveillance colonoscopy. Each centre will schedule the surveillance colonoscopy using their own system. A second reminder should be sent if the patient does not schedule the follow-up colonoscopy within 6 months of the first invitation.

8. QUALITY ASSURANCE OF SURVEILLANCE COLONOSCOPY

All EPoS centre are required to have an established system for quality control monitoring for endoscopy and histopathology services. This may include:

- Continuous monitoring of performance for centres and endoscopists
- Detection rates (polyps, cancers)
- Cecum intubation rate, withdrawal time, procedure time
- Use of sedation

- Complications and adverse effects
- Satisfaction of screenees with endoscopists/personnel/logistics
- Pain and discomfort during and after the screening examination
- Sample studies for histopathologic review of removed polyps

9. ETHICS

The study will be submitted for approval by the ethical committees at each participating centre. All individuals will provide written informed consent before enrolment.

10. STUDY MONITORING

10.1 ROUTINE MONITORING

The central data management office will be responsible for implementing quality control systems for the data collected. This will include checks on data values at the time of data entry (or, if data is transferred in batches, at the time that the data is uploaded into the central database). More complex central checks will also be conducted and any relevant queries sent to the participating centres in a timely way.

10.2 DATA SAFETY AND MONITORING BOARD (DSMB)

In addition to the routine monitoring described in section 10.1, there will be an Independent Data Safety and Monitoring Committee (DSMB) which will review the safety data at regular intervals, and the endpoint data at the defined intervals. The DSMB will also ensure that the study is conducted to required ethical standards. The members of the DSMB will be appointed by the Study Principal Investigators and must not be involved in the Study in any way. At least one statistician will be appointed to the Board, and the activities of the Board will be coordinated by the central data management office.

11. STATISTICAL ANALYSIS PLAN

Participants are followed for the primary endpoint (incidence of CRC), until death/incidence of CRC or end of follow-up, whichever happens first. All randomised participants are followed up through national or regional registries, regardless of whether they continue in the study or not. The primary analytic approach of the trial will follow the intention-to-treat (ITT) principle. We will compare the ~~average rate~~

~~of differences for~~ each endpoint between the intervention groups by calculating risk differences and log-rank test ~~fitting a Cox proportional hazards model~~. The limit for the statistical significance will be established in 0.05 and 95% confidence intervals will be calculated. If the distribution of any baseline characteristics is found to be imbalanced between the arms, we will conduct a sensitivity analysis in which those characteristics will be included as covariates in the model.

We will also do analyses to estimate the causal effect that would have been observed if all individuals in the intervention arms had been compliant. We will refer to these analyses as “adherence-adjusted” analyses. We will use two different analytic approaches to obtain “adherence-adjusted” estimates: instrumental variables methods and inverse probability weighting. For comparability, we will translate the estimates from both approaches into a common metric: adjusted (CRC-free) survival curves. To implement instrumental variables methods (with the indicator for treatment arm as the instrument), we will use g-estimation of nested structural models. To implement inverse probability weighted estimation, we will estimate the weights and the parameters of a marginal structural Cox model. The estimation of inverse probability weights in one intervention arm requires the measurement of variables that jointly predict compliance with the baseline intervention and the endpoint. These variables include age, sex, baseline findings, physical activity, family history of colorectal cancer, smoking status, use of aspirin, NSAIDs, and hormone replacement therapy (9).

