3.2 SECONDARY ENDPOINTS

The following endpoints will also be compared in the different arms in EPoS I and II, and in EPoS III

- Colorectal cancer mortality
- Cost-effectiveness
- Yield of advanced adenomas, adenomas and serrated polyps
- Adverse events within 30 days of colonoscopy (defined as bleeding requiring transfusion or hospitalization, perforation, death or other colonoscopy-related events)
- Differences regarding indication of baseline colonoscopy

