4.1.2. Time of surveillance colonoscopies

Surveillance colonoscopies are scheduled at the participating centres according to the time slots defined in the protocol for the different study groups and arms (see below). For all participating patients, a reminder will be sent by the EPOS database management team to the national coordinators and the study-administration of the participating centres approx. 4-6 months before the surveillance colonoscopy is scheduled.

Surveillance colonoscopies are to be performed within a 6-month time interval from the protocol-defined date. Surveillance colonoscopies which are performed earlier than 6 months before or later than 6 months after the protocol-defined date are recorded as a protocol deviation (but results as well as reason for deviation are to be recorded in the trial database).

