11.1 Power rationale and Ethical considerations

Because removal of precursor lesions is assumed to prevent development of invasive cancer, it is implausible that less intense colonoscopic surveillance following adenoma removal would entail a lower cumulative incidence of colorectal cancer than more frequent surveillance. Such an outcome would, however, arise if the preventive effect of more frequent surveillance (with removal of incident adenomas) is outweighed by overdiagnosis of invasive cancer. A similar, or even identical, cumulative incidence of colorectal cancer following more or less frequent surveillance is theoretically possible, notably if the average progression time from a detectable precursor lesion (adenoma) to invasive cancer are longer than the different surveillance intervals applied in the EPoS trials. However, trials designed to document equivalence would require unrealistically large sample sizes and are therefore unlikely to ever be undertaken.

We considered as the most plausible outcome of the EPoS trials a slightly, perhaps only marginally, higher cumulative incidence of colorectal cancer with less than with more frequent colonoscopic surveillance. As a corollary, our two studies named EPoS I and EPoS II are both designed as non-inferiority randomized trials.

There are several reasons why trials designed to test this hypothesis are considered ethically justifiable:

- Firstly, colonoscopy carries risks, chiefly caused by bleeding or perforation of the colon. Although such complications are rare, notably in high quality settings, they are severe and sometimes life threatening. Hence, complications might substantially counteract the possible survival benefit of more intense surveillance which, in absolute terms (number of lives saved per colonoscopy) is small anyway.
- Secondly, screening to detect precursor lesions and invasive cancer may entail overdiagnosis and overtreatment of lesions that would never have progressed to a lethal stage during the individual's remaining lifetime. The probability of overdiagnosis is likely to be positively correlated with the number of surveillance colonoscopies. Although the extent of overdiagnosis is poorly quantified for colonoscopic screening, it is substantial for other, more established, screening tools such as PAP-smear for cervical cancer, mammography for breast cancer and prostate-specific antigen (PSA) for prostate cancer.

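### Section 11 sets a margin-free log-rank test beside the risk difference without saying which decides, and applies it to polyp yield, where it responds to the examination schedule for common findings

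*Protocol*

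**What the plan says.** Section 11 (Statistical Analysis Plan) of the protocol says the trials will compare "each endpoint between the intervention groups by calculating risk differences and log-rank test". It continues: "The limit for the statistical significance will be established in 0.05 and 95% confidence intervals will be calculated". No margin appears there, and nothing ranks the risk difference against the log-rank test.

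The sample size section, also numbered 11, works by "using a non-inferiority hypothesis with an equivalence interval of 0.5% for patients with low risk adenomas and 0.7% for patients with high risk adenomas". Section 11.1 states that "our two studies named EPoS I and EPoS II are both designed as non-inferiority randomized trials". It ties the decision to an interval: the null hypothesis is to be "rejected only if the upper limit of the 95% confidence interval for the absolute difference in cumulative incidence of colorectal cancer" at ten years goes beyond 0.5% (EPoS I) or 0.7% (EPoS II).

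Section 3.2 lists, among the endpoints to be compared between arms, "Yield of advanced adenomas, adenomas and serrated polyps". Sections 4.3.1 and 4.3.2 schedule the arms differently. EPoS I examines at years 5 and 10 against year 10 only. EPoS II examines at years 3 and 5 against year 5, and then both arms at year 10.

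**The concern.** The log-rank null is equal hazards. A non-significant result therefore does not show that the longer interval is within the margin. Section 11 puts this test on the same footing as the risk difference and never points to the rule in section 11.1, so a reader of section 11 cannot tell which result settles the primary question. Section 11.1 regards a slightly higher cancer incidence with less surveillance as the most plausible outcome. That is the range in which the two results are likely to disagree, and a report of no significant difference would favour the longer interval.

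Yield raises a separate problem. A polyp enters the data only when someone looks. If the arms are examined in different years, time to detection differs between them even when the lesions do not. A log-rank test on that time would then report a difference produced by the calendar.

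**Working it through.** **Inputs.** From the sample size section: 10-year cancer risk in the shorter-interval arm 1% and 2%; margins 0.5% and 0.7%; 6,783 and 6,852 per arm; 90% power; one-sided alpha 0.05. Examination years are from sections 4.3.1 and 4.3.2. Polyp yields are assumed, because the protocol gives none.

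**1. What the trials are sized for.** With true difference zero, n per arm = (z₁₋α + z₁₋β)² × 2p(1−p)/δ².
- EPoS I, 90% power: (1.645 + 1.282)² × 0.0198/0.005² = 6,782.6, so 6,783.
- EPoS II, 90% power: (1.645 + 1.282)² × 0.0392/0.007² = 6,851.1, so 6,852.
- At 80% power the formula gives 4,897 and 4,947.

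All four figures in Table 2 are reproduced. A two-sided equality test of 1% against 1.5%, or 2% against 2.7%, would need 10,375 and 9,840 per arm for 90% power. The design is built on the risk difference and its margin.

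**2. Equality test when the true difference equals the margin.** At event rates of 1–3% a two-proportion test is a close stand-in for the log-rank test. Power = Φ[(δ − 1.96·SE₀)/SE₁], with SE₀ pooled and SE₁ unpooled.
- EPoS I: SE₀ = 0.1908%, SE₁ = 0.1907%; (0.5 − 0.3739)/0.1907 = 0.661; power 74.6%, so non-significant in 25.4%.
- EPoS II: SE₀ = 0.2588%, SE₁ = 0.2587%; (0.7 − 0.5073)/0.2587 = 0.745; power 77.2%, so non-significant in 22.8%.

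In 200,000 simulated trials per setting, the 95% interval rule wrongly declared non-inferiority at the margin in 2.6% (EPoS I) and 2.5% (EPoS II). With a true difference of half the margin, 43% and 42% of trials were non-significant and also failed the interval rule. No simulated trial was significantly worse and yet non-inferior, so at these sizes and risks the disagreement runs one way.

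**3. Log-rank test on yield, same cumulative yield in both arms.** EPoS I, 40% yield by year 10, half of Group 1's found at year 5:
- Year 5: 1,356.6 events in Group 1, none in Group 2. Observed minus expected in Group 1 = 678.3; variance 305.3.
- Year 10: at risk 5,426.4 and 6,783; events 1,356.6 and 2,713.2. Expected in Group 1 = 4,069.8 × 5,426.4/12,209.4 = 1,808.8. Observed minus expected = −452.2; variance 670.0.
- Z = (678.3 − 452.2)/√(305.3 + 670.0) = 226.1/31.2 = 7.2.

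The Z column repeats this calculation at other yields. The rejection columns come from 20,000 simulated trials per setting with a constant lesion hazard, equal in both arms.

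| Assumed cumulative yield | EPoS I Z | EPoS I log-rank rejects (by year 10) | EPoS II log-rank rejects (by year 5) |
|---|---|---|---|
| 5% | – | 5% | 6% |
| 10% | 0.7 | 11% | 13% |
| 15% | – | 30% | – |
| 20% | 2.2 | 63% | 73% |
| 30% | 4.4 | 99.6% | about 100% |
| 40% | 7.2 | 100% | 100% |

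For EPoS II through year 10, with assumed cumulative yields of 24/35/50% by years 3/5/10, Z = 5.9. In the same simulations a comparison of cumulative proportions through the common visit rejected in 4.7–5.3% of trials at every yield from 1% to 50%.

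**4. Findings at the common examination alone.** In the 40% scenario, first findings at year 10 are 20% in Group 1 and 40% in Group 2, because Group 1 was already examined and cleared at year 5. Z = 0.20/√(0.30 × 0.70 × 2/6,783) = 25. That comparison reflects the schedule even more strongly than the log-rank test does.

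**The case against.** The strongest reply is that non-inferiority on cancer does not rest on the log-rank test. The same sentence names risk differences first, the next adds 95% confidence intervals, and section 11.1 sets the upper limit against the margin. This stands. A reader might infer that the protocol would conclude non-inferiority from a non-significant log-rank test. Nothing in it says so, and the 25% and 23% would be error rates only under that unstated rule. They show what the log-rank test cannot do, not how often the plan would err.

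On yield, a reader might infer that the log-rank test would produce false differences for every type of lesion. The calculations do not support that: at 5% the distortion is not visible, and at 10% it is slight. The protocol also never defines yield as time to first detection, and its reference to every endpoint is loose, since cost-effectiveness is on the same list. These points limit the claim. They do not remove it, because yield is listed for comparison between arms and the log-rank test is assigned to all endpoints.

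It may also be said that such detail belongs in a separate statistical analysis plan, which is not at hand. But the issue is not missing detail: section 11 already states a test and a significance limit, and that test does not match the design described in the following sections.

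**Conclusion.** The point holds in a limited form. Section 11 pairs a test that contains no margin with the risk difference, without citing the margin or saying which result decides, while the sample size section and section 11.1 rest wholly on the risk difference. For cancer this is an ambiguity that can be cleared up, because a suitable interval rule already exists in section 11.1. For yield, the log-rank test is unsuitable for common findings: schedule alone makes it significant in 63% (EPoS I) to 73% (EPoS II, year 5) of trials at 20% yield and in nearly all at 30%.

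The cancer figures assume the protocol's own risks and group sizes, a two-sided 0.05 test (section 11 does not state sidedness) and the two-proportion approximation. The 2.5% uses the 95% interval of section 11.1; the one-sided 0.05 of the sample size would correspond to 5%, a mismatch that is a separate matter. The yield figures assume full attendance at the scheduled years, perfect detection, no regression of lesions, first detection as the event, and no extra examinations prompted by earlier findings.

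**What to change.** In section 11, state that the primary analysis in EPoS I and II is the difference in 10-year cumulative colorectal cancer incidence, longer minus shorter interval, with its confidence interval compared with 0.5% or 0.7%, and refer to section 11.1. Keep the log-rank test for cancer as supportive only.

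Set the horizon so that it takes in the 10-year examination and its full window in both arms. Section 4.1.2 says "Surveillance colonoscopies are to be performed within a 6-month time interval from the protocol-defined date", and sections 4.3.1 and 4.3.2 place the analysis after that examination, so cancers found at it are evidently meant to count. A cut at exactly ten years would lose those found in the later half of the window.

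For yield, drop the log-rank test. Compare the cumulative proportion of participants with each finding after baseline through the common visit: year 10 in EPoS I, years 5 and 10 in EPoS II. Report findings at the common examination alone as descriptive, because the shorter-interval arm has already been cleared once.

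The cost is a few sentences and no new data. The change should be made before outcomes by arm are seen.
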